- To assess the efficacy of Lambda (180 mcg SC injections) vs. saline placebo injection in inducing PCR negativity at days 3, 7 and 14 among hospitalized subjects with symptomatic COVID-19 infection
- To assess the efficacy of Lambda (180 mcg SC injections) vs. saline placebo injection in inducing symptomatic improvement in subjects with COVID-19 infection, assessed by daily symptom questionnaire
- To assess the efficacy of Lambda (180 mcg SC injections) vs. saline placebo injection in improving clinical outcomes (death, ICU stay, intubation) in subjects hospitalized with COVID-19 infection
- To evaluate the safety and tolerability of Lambda (180 mcg SC injections) vs. saline placebo injection

III. Study Design

This is a prospective randomized trial to assess the antiviral efficacy of Lambda (180 mcg SC injection) vs. standard of care in up to 20 subjects hospitalized with COVID-19 infection.

Visit schedule

After referral by the care team and informed consent, and once the subject is confirmed as COVID-19 positive on clinical testing, patients will have initial clinical lab testing performed during baseline (visit 1). After confirmation of inclusion criteria, patients will be randomized 1:1 to receive the first dose of Lambda or saline placebo at the baseline visit (visit 1). Nasal swabs for PCR analysis will be collected for all subjects on Days 3, 7 and 14. An optional Day 5 nasal swab collection will occur only for subject who remain hospitalized on Day 5. On day 7, subjects in the treatment arm will receive a second Lambda injection and subjects in the control arm will receive a second saline placebo injection. On Day 14, subjects will undergo laboratory measurements to confirm CBC and LFT values are within safe parameters. Research blood will be collected and stored for future testing to measure levels of pro-inflammatory cytokines (e.g. IFN- γ , IL-6, IP-10, MCP-1, TNF- α). Measurements will be performed using excess blood collected for clinical purposes wherever possible. Subjects will complete a daily symptom questionnaire from screening through Day 14 ([Appendix 5](#)).

Administration of Treatment

Upto an initial 30 hospitalized patients will be enrolled (consented), with a goal of 20 subjects randomized 1:1 to receive either Lambda 180 mcg SC injections or saline placebo injections.

Administration of first dose Lambda/placebo in relation to initial COVID-19 symptom onset will be documented in all subjects.

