- a. Historic diagnosis by PCR test may be at any time prior to hospitalization but subject must have documentation of a positive SARS-CoV-2 RT-PCR test within 72 hours of randomization
4. Female subjects of childbearing potential who engage in heterosexual intercourse must agree to use protocol specified method(s) of contraception as described in [Appendix 4](#)
5. Subject must be able to comply with the dosing instructions for study drug administration and able to complete the study schedule of assessments

Exclusion Criteria

1. Current or prior history of any of the following:
 - a. Clinically-significant illness or any other major medical disorder that in the opinion of the investigator, may interfere with subject treatment, assessment or compliance with the protocol
 - b. Treatment with IFN or other immunomodulatory/immunosuppressive agent within 12 months before screening.
 - c. Respiratory compromise requiring ventilatory support other than nasal cannula (mask, bipap or intubation and mechanical ventilation).
 - d. History of treatment with any of the following medications within five half-lives or 30 days before administration of the study drug (whichever is longer): anti-IL-6, anti-IL6R antagonists, Janus kinase inhibitors, ustekinumab (anti-IL-12/23), or anti IL-23 agents (guselkumab).
2. Pregnant or Nursing Females (a negative pregnancy test (urine or serum) is required during screening [if historic negative result within 48 hours prior to consent is not available] for WOCBP)
3. Life threatening SAE during the screening period
4. Subjects having the following laboratory parameters at screening
 - a. Platelet count <90,000 cells/mm³
 - b. WBC count <3,000 cells/mm³
 - c. ANC <1,500 cells/mm³
 - d. Hb <11 g/dL for women and <12 g/dL for men
 - e. CrCl < 50 mL/min
 - f. Direct Bilirubin level $\geq 1.5 \times$ ULN
 - g. INR ≥ 1.5 (except in the setting of concomitant anticoagulant use)
 - h. CRP >200 mg/L
5. Females who may wish to become pregnant and/or plan to undergo egg harvesting during the course of the study and up to 30 days of the last dose of study drug. WOCBP must abstain from breastfeeding and be willing to use effective birth control during through the week 4 post treatment follow-up visit.
6. Clinically-relevant alcohol or drug abuse within 12 months of screening. Use of any prohibited concomitant medications as described in [Section V](#)
7. Known hypersensitivity to IFN

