8. Current or planned participation in an investigational new drug (IND) trial from 30-days prior to randomization through Day 14 post treatment.
9. History of full COVID-19 vaccination
 - a. Full vaccination is defined as >2 weeks post final vaccination dose

V. Investigational Product

Randomization, Blinding and Treatment Codes

This is a randomized, single-blinded controlled study. Subjects will be randomized 1:1 to receive Lambda 180 mcg SC injections vs. saline placebo injections.

Description and Handling

Lambda Formulation

Lambda injection is a sterile, nonpyrogenic, ready to use solution (0.4 mg/mL) that is clear to opalescent, colorless to pale yellow, and is essentially free of particles. Lambda injection is provided in a 1-mL long Type I glass syringe with a 29-gauge, ½-inch, thin-walled needle. The syringes are prefilled with a solution of Lambda Injection, mannitol, L-histidine, polysorbate 80, hydrochloric acid, and water for injections; they are intended for a single use (180 mcg dose). The study drug will be donated by Eiger Biopharmaceuticals. Swab kits and RT-PCR testing will be supplied by a contract research organization, Viroclinics.

Lambda Packaging and Labeling

Storage of the study drug will be done in the Massachusetts General Hospital Clinical Trials Pharmacy (MGH CTP) (directed by [name], PharmD). Study drug will be packaged and labeled per the Massachusetts General Hospital Investigational Pharmacy standard procedure and will adhere to federal guidelines.

Lambda Storage and Handling

Prefilled syringes should be stored in a refrigerator at 2 - 8°C (36 - 46°F) and protected from long-term (>24 hours) exposure to light. Lambda Injections should not be frozen. Until administered to the subjects, syringes containing the study drug should be stored in a secure area, accessible only to authorized site personnel or vendor (in the case of home health visits). During transport to subject homes (via ambulance vehicle for home health visits only), drug should be stored in a cooler with an ice pack. To ensure the stability and proper identification, study drugs should not be stored in a container other than the container in which they were supplied.

Saline Placebo

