Study staff, along with the MGH-established COVID Recruitment team, will review patients in the MGH ED and current admitted patient charts to identify candidate subjects, ideally within the first 24 hours of their admission and/or positive COVID PCR test. Upon identification of a potential subject, the COVID Recruitment team will notify the study team via email regarding a potentially eligible patient. Study staff will prescreen the chart for eligibility and upon confirmation of presumed eligibility, a physician investigator will immediately contact the clinical care team and provide them with information regarding the study. A member of the clinical care team who is already known to the patient will gauge the appropriateness of approaching them. If they deem it appropriate, the clinical care team member will approach the patient to determine if they are willing to learn about this study. If the patient agrees, the clinical care team member will authorize the study staff to approach the patient to discuss the study. The described process is expected to take place within 48 hours of the most recent positive COVID-19 PCR test.

NOTE: per the MGH COVID Recruitment team policy (memo dated 01May2020), any potentially eligible subject identified directly by study staff must be referred back to the team who will then distribute the potential participant accordingly across recruiting COVID trials.

Patients will be consented according to the Partners IRB's Guidelines for Consenting in COVID Research that is More than Minimal Risk. Participants will be enrolled, randomized and dosed from the inpatient floors. In cases with randomized subjects are discharged prior to study completion, home visits with an appropriately credentialed and trained provider (paramedic or registered nurse) will be utilized as available to limit study specific outpatient visits whenever possible. **NOTE: all Day 0 visits (first dose of Lambda/Placebo) must occur onsite at MGH.**

Pretreatment and Baseline Assessments

Baseline Visit

Subjects will be screened no later than within 48 hours of their initial hospital presentation to determine eligibility and provide informed consent for participation in the study.

The following will be performed and documented during screening to assess eligibility

- Obtain informed consent
- Determine inclusion and exclusion eligibility
- Obtain relevant medical history
- Obtain details of concomitant medications

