This is a pilot study to assess the ability of Lambda to increase the proportion of subjects with PCR negativity at Day 7 compared to standard of care (placebo group) as a primary endpoint. We anticipate that no subjects in the standard of care arm will be PCR negative at Day 7, and we anticipate that 50% of subjects in the Lambda arm will be PCR negative at Day 7.

The treatment will be considered for further study if the proportion of subjects who achieve PCR negativity will be 30% higher at Day 7 in the Lambda arm compared to the standard of care arm. This would correspond to 3/10 subjects in the Lambda arm if 0/10 subjects were PCR negative in the standard of care (placebo) arm. Assuming 50% of subjects will be PCR negative, we have a 94% chance of observing 3 or more subjects who are PCR negative at Day 7. This shows that our sample size of 10 subjects per group is sufficient to have a reasonable chance to support further study given the proposed treatment effect. Additionally, demonstration of a reduction in viral load relative to the placebo arm will be factored into decisions to pursue further trials.

IX. References

3. Loutfy MR et al. Interferon alfacon-1 plus corticosteroids in severe acute respiratory syndrome: A preliminary study. *JAMA* 2003 Dec 24/31; 290:3222-8.

Appendices

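### Time from symptom onset to first dose is recorded for every subject but used in no analysis, although entry sets no limit on illness duration and a chance stage imbalance could distort a 10-per-arm result

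*Combined protocol and SAP*

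**What the plan says.** Section IV, Inclusion Criterion 3a, places no limit on when infection began: "Historic diagnosis by PCR test may be at any time prior to hospitalization". The same criterion adds that the "subject must have documentation of a positive SARS-CoV-2 RT-PCR test within 72 hours of randomization". Section VI (Baseline Visit) ties screening to hospital arrival: "Subjects will be screened no later than within 48 hours of their initial hospital presentation". No criterion caps days since symptom onset or since the first positive test.

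Section III (Administration of Treatment) provides for the timing to be captured: "Administration of first dose Lambda/placebo in relation to initial COVID-19 symptom onset will be documented in all subjects". Section V describes allocation by ratio only: "Subjects will be randomized 1:1 to receive Lambda 180 mcg SC injections vs. saline placebo injections". No stratification factor is named.

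Section VIII compares Day 7 PCR negativity with an unadjusted Fisher's exact test. It compares change in quantitative PCR from baseline to Day 7 with a two-sample t-test, and symptom scores with a linear mixed model for which no covariate is named. Onset timing appears in none of these, nor in the log-rank and Cox analyses. The sample size text supports further study if Day 7 negativity is 30 points higher on Lambda, illustrated as 3/10 against 0/10. It rests on two premises. The one for placebo reads: "We anticipate that no subjects in the standard of care arm will be PCR negative at Day 7". For Lambda, the expected Day 7 rate is put at one half.

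**The concern.** A subject in the first days of illness and a subject who has been PCR positive for much longer can both enter. If the chance of turning negative by Day 7 without treatment depends on illness stage, part of the spread in the primary and viral-load outcomes comes from a baseline characteristic that the protocol already records. In a trial of 20, that characteristic can fall unevenly between the arms. The go signal is a raw difference that three subjects can decide, so a reader of the result would want to know whether the arms had similar onset times. As written, the plan neither adjusts for onset time nor commits to showing it by arm. It also forgoes whatever precision the variable could add to the viral-load and symptom models.

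**Working it through.** **Inputs from the documents.** 10 per arm; Lambda 50% and placebo 0% negative at Day 7; go criterion of at least 3 more negatives among 10 on Lambda than among 10 on placebo.

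**Inputs assumed.** The documents give no clearance rate by stage, so several late/early pairs are shown, with K = 6 or 10 late-stage subjects among 20. Two-sided 0.05 is assumed for Fisher's test, because Section VIII states neither level nor sidedness.

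**Step 1: the plan's figure.** P(at least 3 of 10 | 0.5) = 1 − (1 + 10 + 45)/1024 = 94.5%, which agrees with the stated 94%.

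**Step 2: how often stage is unbalanced.** With 10:10 allocation, the number X of late-stage subjects on Lambda is hypergeometric: P(X = x) = C(K,x)·C(20−K,10−x)/C(20,10), where C(20,10) = 184,756.

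- K = 6, four or more extra late-stage subjects on Lambda (X = 5 or 6): (12,012 + 1,001)/184,756 = 7.0%. Either direction: 14.1%.
- K = 10, X = 7 or more: (14,400 + 2,025 + 100 + 1)/184,756 = 8.9%. Either direction: 17.9%.

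**Step 3: false-go rate over all randomisations.** Each arm's count of negatives is a sum of two binomials (late and early subjects). P(difference ≥ 3) is averaged over X with no drug effect. The comparator is a homogeneous population with the same mean clearance, for example (6 × 0.50 + 14 × 0.05)/20 = 18.5%.

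| Late/early clearance | K | Mean | Mixed stages | Homogeneous, same mean | Stage exactly balanced |
|---|---|---|---|---|---|
| 50%/5% | 6 | 18.5% | 7.4% | 7.2% | 4.1% |
| 50%/5% | 10 | 27.5% | 10.6% | 10.4% | 7.2% |
| 40%/0% | 10 | 20% | 8.0% | 7.8% | 5.1% |
| 60%/0% | 10 | 30% | 11.3% | 11.0% | 5.1% |
| 30%/10% | 10 | 20% | 7.9% | 7.8% | 7.2% |

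Mixing stages adds about 0.2 points at 50%/5%, and between under 0.1 and about 0.3 points across the table. Nearly all of the false-go rate comes from non-zero placebo clearance with 10 per arm. Exact balance would remove about 3 points at 50%/5% but under 1 point at 30%/10%.

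**Step 4: the single realised trial (K = 10).** A 7:3 split shifts the expected difference by (0.7 − 0.3) × (late rate − early rate). At 50%/5% this is 0.4 × 0.45 = 18 points, set against a 30-point criterion. Below, the effective drug is assumed to clear half of those who would otherwise stay positive.

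| Late/early clearance | Inert drug, go at 5:5 | Inert drug, go at 7:3 towards Lambda | Effective drug, go at 5:5 | Effective drug, go at 3:7 (more late on placebo) |
|---|---|---|---|---|
| 50%/5% | 7% | 34% | 73% | 46% |
| 40%/0% | 5% | 28% | 79% | 56% |
| 60%/0% | 5% | 48% | 71% | 34% |
| 50%/10% | 9% | 31% | 70% | 47% |
| 30%/10% | 7% | 16% | 78% | 68% |

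**Step 5: the formal test.** Under a common clearance rate of 0% to 50%, the two-sided error of Fisher's test is at most 1.3%. A result of 3/10 against 0/10 gives p = 0.21, so the go criterion is not a test and lacks that protection.

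**The case against.** The strongest case against is that randomisation already deals with this. The primary test is valid whatever the mix of stages, and step 3 shows that the overall false-go rate is almost the same as in a homogeneous population. That stands.

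The imbalance figures of 14.1% and 17.9% count both directions. The direction that mimics benefit has half that probability, so a split of that size is not the usual outcome. That also stands.

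The plan is not blind to baseline status. A pre-dose swab is taken, the key secondary analysis uses change from baseline, and viral-load reduction feeds into the decision on further trials. This answers part of the concern, but baseline load is not illness duration, and a change score fixes the weight given to baseline instead of estimating it. Entry is also narrowed by the 72-hour positive test, the 48-hour screening window, the limit on ventilatory support and the CRP ceiling. None of these caps time since onset.

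A reader might infer that subjects with an old first diagnosis are near natural clearance, or that 0% placebo clearance is tenable only for early-stage entry. The documents say neither. Stage-dependent clearance is a reasonable premise whose size is unknown here.

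A reader might also infer that randomisation must be stratified. The documents do not compel that. They give no cut-point and do not say when onset timing is recorded. Enrolment halts once 10 subjects are on Lambda, so incomplete blocks in two strata could close the trial with fewer than 10 on placebo.

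**Conclusion.** The point holds as a modest, inexpensive improvement to the analysis. The documents settle three facts: entry does not limit time since infection or onset, the onset-to-dose interval is recorded for everyone, and Section VIII does not use it.

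It would be wrong to conclude that mixed illness stage biases the trial or materially inflates its overall error; at 50%/5% it adds about 0.2 points to the false-go rate. The exposure is conditional. In the roughly 7% to 9% of trials where Lambda receives at least four more late-stage subjects, the raw 30-point signal can owe much to the split, and in an equal share of trials a real effect can be obscured. How much depends on the stage gradient. At K = 10 and a 7:3 split, the inert-drug go probability is 16% at 30%/10% and 48% at 60%/0%. All stage-specific rates and values of K are assumptions. Whether 0% placebo clearance is realistic is a separate question, and it accounts for most of the false-go rate.

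**What to change.** Amend Section VIII before any outcome is examined by arm:

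- Replace the Day 7 two-sample t-test on change in quantitative PCR with an ANCOVA on Day 7 viral load, with treatment, baseline viral load and days from symptom onset to first dose as terms.
- Add days since onset as a covariate in the symptom mixed model.
- Beside the go criterion, report days since onset by arm and Day 7 negativity by arm within an early/late split. Fix the cut-point in advance, without reference to allocation.
- State how a subject without an onset date is handled, so that time since first positive test is not mixed silently with time since onset.
- Keep Fisher's exact test as the primary analysis.

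No new data item and no eligibility change is needed. With 20 complete subjects, residual degrees of freedom in the viral-load comparison fall from 20 − 2 = 18 to 20 − 4 = 16, and the mixed model gains one parameter. If onset time does not predict outcome, precision falls slightly. The early/late table will have small cells and is descriptive only. Stratifying randomisation in two levels remains an option, with the enrolment-cap difficulty noted above, but this point does not require it.

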In this single blind study, saline placebo injections will be prepared by the MGH CTP. Under the direction of the lead pharmacist, pharmacy staff will prepare the placebo injections by drawing up approximately 0.45 ml of sterile saline into a 1 ml Monoject Tuberculin Safety Syringe with a 28 gauge, ½ inch, thin walled needle. Placebo injections will be labeled with standard MGH research prescription EPIC label as peginterferon lambda-1a or placebo however the display name and administration instructions will be unblinded for provider to be able to choose the correct treatment.

Lambda/Placebo Administration

Each dose of study drug will be dispensed by the MGH CTP in the form of pre-filled syringes. Appropriately delegated, trained and credentialed study staff or contracted study vendor (in the case of home health visits) will administer the stud drug by subcutaneous injection. The injection site should be documented and entered into the EDC. The injection site may be any of the following locations:

- Upper outer arm (right/left)
- Front outer upper thigh (right/left)
- Abdomen
- Upper hip (Right/Left)

For active Lambda treatment only: prior to administration, credentialed staff will expel the air bubble from the syringe and set the dose by aligning the front edge of the stopper with the correct dose indicator line (180 mcg).

Prior and Concomitant Medications

Concomitant medications taken within 30 days prior to screening, up to and including 30 days after the last dose of study drug, need to be recorded in the source documents and electronic case report form(s) (eCRFs).

In drug-drug interaction studies in healthy subjects, the activity of select CYP enzymes were evaluated and suggest that following a single 180µg dose, Lambda is a mild inhibitor of CYP1A2, CYP2C9, and CYP3A4 and a moderate inhibitor of CYP2C19 and CYP2D6. Because the effects of these sensitive CYP substrates are mild or moderate, dose adjustments for other concomitant CYP substrates may not be necessary, but should be used with caution.

Accountability for Lambda/Placebo

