Extra consideration will be made regarding fever as an adverse event. Fever is noted as a less common (<10%) potential side effect of Lambda, as well as a common expected symptom of COVID-19 infection. To best distinguish between fever associated with COVID-19 and Lambda treatment emergent or exacerbation of fever, study investigators will adjudicate suspected causality by reviewing time elapsed

between Lambda administration and onset/exacerbation of fever. We acknowledge that this distinction cannot be made with complete accuracy.

Assessment of Severity

The severity grading of AEs will be assessed as Grade 1, 2, 3, 4, or 5 according to the Common Terminology Criteria for Adverse Events (CTCAE) Version 4.03, which can be found at http://evs.nci.nih.gov/ftp1/CTCAE/CTCAE_4.03_2010-06-14_QuickReference_8.5x11.pdf.

For AEs associated with laboratory abnormalities, the event should be graded on the basis of the clinical severity in the context of the underlying conditions; this may or may not be in agreement with the grading of the laboratory abnormality.

The distinction between the seriousness and the severity of an adverse event should be noted. Severe is a measure of intensity; thus, a severe reaction is not necessarily a serious reaction. For example, a headache may be severe in intensity, but would not be classified as serious unless it met one of the criteria for serious events listed above.

Reporting of Adverse Events

The Principal Investigator ([name]) will be immediately notified of any adverse events. These will be documented in detail in the Adverse Events Tracking Log and submitted each year at the time of continuing review. Adverse events will be reported to the PHRC as described in the PHRC policy on Unanticipated Problems Involving Risks to Subjects or Others.

VIII. Statistical Considerations

Data Analysis

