All subjects will be included in the primary intention-to-treat analysis as well as the analyses of secondary outcomes and observed safety events. The primary analysis will compare the proportion of subjects who are PCR negative at post-treatment Day 7 between subjects receiving Lambda vs. standard of care using Fisher's exact test, and the difference between the treatment groups will be estimated using the difference in proportions. Subjects who die during follow up will be considered not to have achieved viral clearance, for the purposes of statistical analysis. Subjects who are lost to follow up will be removed from the analysis, since we consider loss to follow up as being unrelated to our outcome of interest. A key secondary analysis will compare the mean change in quantitative PCR from baseline to Day 7 in the treatment group and placebo group using a two-sample t-test. This analysis will likely have more power to detect a treatment effect compared to the PCR negative analysis since a continuous outcome will be used.

Additional secondary analyses will compare the proportion of subjects who are PCR negative at post-treatment Days 3, 5, and 14 and the mean magnitude of viral load reduction using the same approach at Day 7. In addition, the time to PCR negativity will be compared using a log-rank test, and the difference between the treatment groups will be estimated using a Cox proportional hazards model. To compare changes in symptom scores over time, a linear mixed model will be used to estimate the difference in the change with time between the two treatment groups at each of the post-baseline timepoints. For safety endpoints, the proportion of subjects who experience each type of event will be compared between the Lambda vs. standard of care groups at Day 14 using Fisher's exact test. Additional analysis

will compare proportions of hospitalized subjects who experience progression of disease as reflected by transfer to ICU or intubation, and the length of stay among hospitalized subjects will be compared using the log-rank test. Subjects who die will be analyzed as having a length of stay censored at one day past the last follow-up date. Hence, subjects who die will be considered as having a greater length of stay than subjects who remain alive for the duration of the study. Statistical analyses will be completed using SAS (SAS Institute 2011, Version 9.4, Cary, NC).

Sample size and power calculation:

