Appendix 5: Symptom Questionnaire

Symptom questionnaire will be available as a paper tool as well as an electronic tool (RedCap survey). Patients may complete electronically and submit to study team (preferably via RedCap, email alternative option) or have the option to complete via interview and answers will be dictated onto the paper form by a caregiver, member of the study team or member of the clinical team. Subjects who cannot read English will complete the questionnaire via interview with study team and interpreter present.

DAILY SYMPTOM QUESTIONNAIRE

Subject ID: _____	Date: _____ <small>(mm/dd/yyyy)</small>	Protocol #: 2020P001083
-------------------	--	-------------------------

This survey asks you to record your daily symptoms. This information will help keep track of how you feel and if your symptoms worsen or improve. Thank you for completing this survey!

For each of the questions below, please circle or mark one number per line to indicate your response as it applies to the last 24 hours (1 day).

	Not at all	A little bit	Some-what	Quite a bit	Very much
Muscle pain (Myalgia)					
Loss of smell (Anosmia).....					
Loss of taste					
Cough					
Shortness of breath (Dyspnea)					
Chills					
Fever (Feeling feverish)					
Repeated Shaking with Chills.....					
Headache					
Sore throat.....					

	
---	--

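### The fever causality rule is timed from Lambda only, and neither those who attribute fever nor those who take symptom interviews are masked, so drug-relatedness and interviewed symptom scores can differ by arm

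*Combined protocol and SAP*

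**What the plan says.** **Masking.** Section V (Randomization, Blinding and Treatment Codes) states: "This is a randomized, single-blinded controlled study". Under Saline Placebo, the label is neutral between the arms, but "the display name and administration instructions will be unblinded for provider to be able to choose the correct treatment". The devices differ. For the active arm, "Lambda injection is provided in a 1-mL long Type I glass syringe"; the placebo is drawn into a "1 ml Monoject Tuberculin Safety Syringe with a 28 gauge" needle. Only the active syringe has an air-bubble and dose-setting step. No section names a masked interviewer or adjudicator, or separates the staff who dose from those who assess.

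**Fever.** Under the fever paragraph in Section VII, "study investigators will adjudicate suspected causality by reviewing time elapsed". The interval to be reviewed is the one "between Lambda administration and onset/exacerbation of fever". The paragraph adds that the distinction from COVID-19 fever cannot be made with full accuracy. The general causality scale just above it asks whether an event is related to Lambda or placebo.

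**Symptoms.** Appendix 5 offers electronic self-completion. The alternative is an interview, in which "answers will be dictated onto the paper form by a caregiver, member of the study team or member of the clinical team". An interview is the only route for anyone unable to read English, with the study team and an interpreter present.

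**Analysis.** Section VIII compares safety events by type with Fisher's exact test and symptom scores with a linear mixed model. It also compares ICU transfer or intubation. For discharge, "length of stay among hospitalized subjects will be compared using the log-rank test".

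**The concern.** A placebo arm helps with subjective outcomes only if the same rule is applied to both arms, preferably by people who do not know the arm. Two steps here fall short.

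First, the fever rule uses the interval since Lambda was given. A placebo subject has no such interval. An investigator who follows the text must improvise for that subject, fall back on the general scale, or treat the question as not applicable. An investigator who knows the arm may also read the same fever differently. At stake are the reported drug-relatedness of fever and the criterion in Section III (Toxicity Based Stopping Criteria) that depends on a Grade 4 event being judged related to study drug.

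Second, an interviewed symptom score may be written down by a team member who knows the arm. Symptomatic improvement is one of the four secondary objectives.

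**Working it through.** **Step 1. The plan's own figure.** The plan gives no number for this point. Its one operating figure, in Section VIII, concerns PCR negativity: the chance of 3 or more successes in 10 at a true rate of 50%. That is 1 − (1 + 10 + 45)/1024 = 968/1024 = 0.945, which agrees with the stated 94% apart from rounding. Nothing below changes it.

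**Step 2. The two causality texts side by side.**

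| Text in Section VII | Arms covered | Time anchor |
|---|---|---|
| General causality scale | Lambda and placebo | Time relationship to drug intake |
| Fever paragraph | Lambda only | Time since Lambda administration |

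The specific rule is narrower than the general one it supplements. For a placebo fever the general scale still applies, but the extra timing review has no start time.

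**Step 3. Where the relatedness judgement goes.**
- Relatedness reports: affected.
- Section III, Grade 4 event related to study drug: affected in principle. How often a fever would reach Grade 4 is not stated.
- Section VIII Fisher test: it counts subjects with each type of event, whatever the attribution. Not affected.
- Background fever: Appendix 2 schedules temperature at baseline and Days 3, 7 and 14 for all subjects, and feeling feverish is a questionnaire item for all. Not affected.
- Day 7 PCR: swabs go to a central laboratory (Section VI). Not affected in this way.

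The documents give no fever frequency by arm and no split by attribution, so I put no figure on this part.

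**Step 4. Who may see the arm when symptoms are recorded.** Section V has delegated study staff or a vendor give the injections, and Appendix 5 lets study team members take interviews. Nothing stops one person doing both. The Day 7 visit in Section VI includes both the questionnaire and the second injection, in no stated order. The baseline questionnaire, by contrast, must precede randomization. So the protocol controls the sequence at baseline but not at Day 7.

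**Step 5. Scale of an interviewer effect (illustration only).** From the documents: n = 10 per arm. Assumed: two-sided 5%, a simple two-sample t-test at one time point in place of the mixed model, no true effect, and interviewers shifting scores by d standard deviations between arms.

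Noncentrality = d × √(n/2) = d × √5; df = 18; critical value 2.101.

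| Average shift d | Noncentrality | Chance of p < 0.05 |
|---|---|---|
| 0.125 (0.25 SD, half interviewed) | 0.280 | 5.8% |
| 0.25 (0.25 SD, all interviewed; or 0.5 SD, half) | 0.559 | 8.3% |
| 0.5 (0.5 SD, all interviewed) | 1.118 | 18.5% |

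The rows for half interviewed halve the mean shift and leave the SD unchanged, which is an approximation. The documents give neither the interviewed share nor any interviewer effect.

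**The case against.** The case on the other side is substantial, and much of it stands.

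- **Single-blinding is declared openly, in a pilot of 20.** The rule for taking Lambda further uses Day 7 PCR negativity, with viral load also considered. None of the outcomes discussed here enters it. This stands and limits the weight of the point.
- **A reader might infer that the placebo arm gives no background rate of fever, or that one fever attributed differently could tip the safety test.** The documents do not support either. The Fisher test ignores attribution, temperature and feverishness are collected in both arms, and the general scale allows a placebo fever to be rated as related.
- **A reader might infer that attribution to Lambda decides whether a fever is recorded.** The visit lists call for serious events and events related to protocol procedures, and Section VII judges procedure-relatedness separately from drug-relatedness.
- **A reader might infer that the ward team deciding ICU transfer and discharge knows the arm.** Section V unblinds the display for an undefined provider. Whether that includes the ward team is neither stated nor excluded, so no finding on length of stay or ICU transfer follows.
- **Interviewed answers are dictated on a fixed five-level scale, a caregiver may be the recorder, and self-completion is available.** This stands. It reduces the scope for influence but does not remove it, least of all for subjects who must be interviewed.

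What survives is the mismatch between the two causality texts and the absence of any masking or separation of roles for fever attribution and interviews.

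**Conclusion.** The point holds in limited form. The fever rule as written cannot be applied to a placebo subject and does not match the general causality scale. Those who apply it are not masked, so drug-relatedness of fever can be judged differently by arm. The effect is confined to relatedness reports and the drug-related Grade 4 criterion, and its size cannot be derived from the documents.

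Interviewed symptom scores carry a separate risk. Under the assumed shift of 0.25 to 0.5 SD, a nominal 5% error becomes about 8% to 19% if every score is interviewed and about 6% to 8% if half are. These figures show scale and are not estimates. Self-completed scores escape interviewer influence, although the different syringes might still let a subject guess the arm.

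The point does not undermine the primary endpoint. It is worth correcting because the correction is nearly free.

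**What to change.** 1. **Section VII, fever paragraph.** Replace the reference to Lambda administration with the study injection (Lambda or placebo). State that the rule applies identically in both arms. Have the investigator adjudicate from a listing, by subject number, of injection times and fever onset or worsening times that does not show the arm.
2. **Appendix 5.** Make self-completion the default. Where an interview is needed, have it done where possible by an existing team member who neither ordered nor gave the injection. Record the mode of completion on each form, so that the symptom analysis can be examined by mode.
3. **Section VI, Day 7 visit.** State that the questionnaire is completed before the second injection. This keeps the sight of that injection out of the Day 7 score; it does not remove knowledge gained at the first.

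The cost is wording in three places, one listing, one extra field and a small scheduling effort. The person giving the injection stays unmasked, and an adjudicator who already knows a subject's arm cannot be made to forget it. Interviewers who have not dosed are asked for only where possible, because guaranteeing them might need extra staff, particularly at home visits.

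I do not suggest masking the display name. It exists so that the provider can select the right treatment, and the Lambda syringe has its own preparation step. No dose, schedule or stopping rule changes.
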